#### **6.14.2.1. Dose Limiting Toxicity**

Dose limiting toxicities (DLT) will be listed for all patients on therapy in Phase 1. DLT-equivalent toxicities will also be listed for all patients on therapy in Phase 1 and Phase 2.

In Phase 1 of the study, dose escalation will be driven by safety using a modified 3+3 scheme, with incorporation of model-based dose escalation (Neuenschwander et al. 2008) to assist in estimation of DLT rate at recommended dose level.

A model-based method that incorporates prior expectations about the dose-toxicity curve and controls for over-dosing probability will be applied to the data at the end of each cohort, which will provide quantitative guidance to the investigators and Lilly CRP to help determine the next dose level. Prior expectations about the dose-toxicity curve will be based on observed DLT rates in Study JJCA. After incorporation of observed DLT rates in this study, the posterior probability of a DLT at each dose level will be categorized to 4 bands:

- under-dosing: the probability of a DLT at a given dose level in (0, 0.20)
- targeted toxicity: the probability of a DLT at a given dose level in (0.20, 0.35)
- excessive toxicity: the probability of a DLT at a given dose level in (0.35, 0.60)
- unacceptable toxicity: the probability of a DLT at a given dose level in (0.60, 1.00)

The model aims to recommend a dose which maximizes the probability of targeted toxicity, while controlling the probability of excessive or unacceptable toxicity to less than 25%. The maximum increment of escalation will be no more than 100%. The exact increment will be determined by the investigators and Lilly CRP and may be less than the model prediction or <100%.

Further details on the derivation of a prior for DLT rate and simulations on the dose escalation model are provided in a separate simulation plan document.

#### **6.14.3. Deaths, Other Serious Adverse Events, and Other Notable Adverse Events**

All deaths in this study, including the reasons for death, will be listed by treatment. The reasons for death will be also summarized separately for on-therapy, within 30 days of last dose of study drug and during the long term follow-up periods.

#### **6.14.4. Clinical Laboratory Evaluation**

Listings of all laboratory results will be provided (using SI units [International System of Units], when available) by treatment, for hematology, chemistry, urinalysis, ECG chemistry, immune phenotype, coagulation, CSF and bone marrow. Normal reference ranges, percent of the result outside of range (result divided by lower limit if result is less than lower limit; result divided by higher limit if result is greater than higher limit) and percent change from baseline will also be included. Selected laboratory parameters may be plotted by time.

Laboratory analytes below/above quantifiable levels (data in the database recorded as “ $<x$ ” and “ $>x$ ”) will be reported as such in listings, and imputed to the lower or upper limit of quantification in any summarise or analyses.

Neutrophils, platelets, lymphocytes, monocytes, eosinophils, basophils, RBC, WBC, Nucleated RBCs (NRBC)/100 WBC blasts and other laboratory parameters of interest to disease status will be plotted by time. Data will be log transformed and the logged ratio to baseline analysed by mixed effect model repeated measures with treatment, cycle, and the interaction of treatment and cycle as fixed effects, with baseline and the interaction of baseline and cycle as a covariate. An unstructured variance covariance matrix will be used, data permitting. Otherwise, the following variance covariance structures will be tested and that with the best fit according to AIC selected: compound symmetry, heterogeneous Toeplitz, first-order autoregressive combined with random patient effect, heterogeneous autoregressive, or heterogeneous compound symmetry. The Kenward-Roger method will be used to estimate denominator degrees of freedom. Geometric means and treatment comparisons with corresponding 95% confidence intervals (CIs) for each cycle will be presented in tabular and graphical displays.

A waterfall plot will be provided for minimum percentage bone marrow blasts by treatment arm, coloured by gene mutation status.

A calculated CTCAE grade using CTCAE v4.0 (or higher) will be provided for all laboratory results which can be used independently of clinical judgment to determine a CTCAE severity grade.

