7.1. Inclusion Criteria

Patients are eligible to be included in the study only if they meet **all** of the following criteria during screening prior to first dose of study drug.

- [1] Have acute T-cell lymphoblastic leukemia (T-ALL) or T-cell lymphoblastic lymphoma (T-LBL).

T-ALL is defined by $\geq 25\%$ of blasts in the bone marrow and expression of at least 2 of the following cell surface antigens:

- CD1a, CD2, CD3 (surface or cytoplasmic) CD4, CD5, CD7, and/or CD8.

If the only T-cell markers present are CD4 and CD7, the leukemia cells must also lack the myeloid markers CD33 and/or CD13.

- [2] T-ALL or T-LBL patients with relapsed/refractory disease. Patients with initial refractory disease should have received at least 2 multi-agent chemotherapy induction regimens. Patients in first or second relapse must have been refractory to at least 1 multi-agent chemotherapy reinduction regimen.
- [3] Have had at least 60 days between prior hematopoietic SCT and first dose of study drug.
- [4] Have a performance status of 0 to 2 on the Eastern Cooperative Oncology Group (ECOG) scale (see [Attachment 5](#)) for adults.
- [5] Lansky score $>50\%$ for patients <16 years old.
- [6] Have adequate organ function:
 - hepatic: bilirubin $\leq 1.5 \times$ the upper limit of normal (ULN) and ALT and AST $\leq 3 \times$ ULN. For patients with liver involvement, ALT and AST $\leq 5 \times$ ULN
 - renal: calculated creatinine clearance ≥ 45 mL/min or a serum creatinine based on age/gender ([Attachment 6](#))
- [7] Are at least:

- Adult Phase 1 Part A and Phase 2: ≥ 16 years old at the time of screening.
- Pediatric Phase 1 Part B: 2 to < 16 years old.

[8a] *Men and women with reproductive potential:* Must agree to use a reliable method of birth control during the study and for 3 months following the last dose of study drug(s) or country requirements, whichever is longer.

[8b] *Females with childbearing potential:* Have had a negative serum pregnancy test ≤ 7 days before the first dose of study drug and also must not be breastfeeding.

[9] Have an estimated life expectancy of at least 2 months and in the judgment of the investigator, will be able to complete at least 2 cycles of treatment.

[10] Have given written informed consent/assent prior to any study-specific procedures.

All patients and/or their parents or legally authorized representatives must sign a written ICF. Assent, when appropriate, will be obtained according to institutional guidelines.

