10.1.2. Primary Efficacy Measure

For T-ALL patients, assessment of efficacy will be consistent with NCCN guidelines for ALL and Cheson criteria (Cheson et al. 2003). The primary endpoints are defined as follow.

A CR is defined as <5% blasts in an aspirate sample with marrow spicules and with a count of at least 200 nucleated cells, along with peripheral blood levels including platelets $\geq 100 \times 10^9/L$ and absolute neutrophil count (ANC) $\geq 1 \times 10^9/L$ and without circulating blasts.

A CRi is defined as fulfilling all criteria for CR except for residual neutropenia ($<1000/\mu\text{L}$) or thrombocytopenia ($<100,000/\mu\text{L}$). The proportion of patients achieving a CRi is defined as the total number of patients achieving a CRi divided by the total number of patients randomized in that arm.

All previous extramedullary manifestations of disease must be absent (eg, lymphadenopathy, splenomegaly, skin or gum infiltration, testicular masses, CNS involvement). The CR rate is estimated as the total number of patients achieving a CR divided by the total number of patients randomized in that arm.

The ORR (CR and CRi) is the sum of patients achieving a CR and a CRi divided by the total number of patients randomized in that arm.

The Revised Response Criteria for Malignant Lymphoma (Cheson et al. 2007) will be used to assess the efficacy of LY3039478 in T-LBL patients followed by CT scan or MRI.

For patients with T-LBL followed by CT/MRI, the criteria for CR is similar to T-ALL and requires the disappearance of all measurable disease, signs, symptoms, and biochemical changes related to the tumor.

For T-LBL patients assessed by PET-CT, the criteria for CR is as follows: complete metabolic response with the lymph nodes or extralymphatic sites having a score of 1, 2, or 3 with or without a residual mass on the 5-point assessment scale with high physiologic uptake or with activation within spleen or marrow (eg, with chemotherapy or myeloid colony-stimulating factors), uptake may be greater than normal mediastinum and/or liver. In this circumstance, complete metabolic response may be inferred if uptake at sites of initial involvement is no greater than surrounding normal tissue even if the tissue has high physiologic uptake. There can be no new lesions and no evidence of FDG-avid disease in the bone marrow.

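### SAP 6.14.4 applies a log-ratio model to blasts and other counts that can be zero, with no rule for a recorded zero; in T-ALL remission the circulating blast count is zero

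*SAP*

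**What the plan says.** SAP 6.14.4 names neutrophils, platelets, several white-cell types and red cells, and ends the list with "Nucleated RBCs (NRBC)/100 WBC blasts and other laboratory parameters of interest to disease status will be plotted by time". A comma seems to be missing before blasts, but Protocol Attachment 2 lists blasts and NRBC as separate hematology items, so blasts are in the list. The next sentence gives the model: "Data will be log transformed and the logged ratio to baseline analysed by mixed effect model repeated measures". Treatment, cycle and their interaction are fixed effects, and baseline and its interaction with cycle are covariates. Results are reported per cycle as geometric means with between-arm comparisons and 95% intervals.

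The only rule for extreme values concerns results stored as <x or >x, which are "imputed to the lower or upper limit of quantification in any summarise or analyses". A recorded 0 is not mentioned. SAP 6.1 leaves missing repeated measurements unimputed and relies on a mixed model for them. It also allows other methods, including nonparametric ones, when assumptions fail.

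Protocol 10.1.2 sets the T-ALL remission criteria. For marrow: "A CR is defined as <5% blasts in an aspirate sample with marrow spicules". For blood, the patient must be "and without circulating blasts". CRi carries the same blast criteria: "A CRi is defined as fulfilling all criteria for CR except for residual neutropenia" or thrombocytopenia. For T-LBL followed by CT/MRI, CR is called similar to T-ALL and "requires the disappearance of all measurable disease, signs, symptoms, and biochemical changes related to the tumor"; no separate circulating-blast count is given. Protocol 7.1 defines T-ALL by a share "of blasts in the bone marrow and expression of at least 2 of the following cell surface antigens", with no minimum in blood.

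**The concern.** The planned calculation cannot be carried out for a patient whose circulating blasts have cleared, because the log of zero is undefined. The usual software result is a missing value. A mixed model then fills the gap, in effect, from patients who still have blasts. Its justification is that missingness is unrelated to the unseen value once the observed data are taken into account. That fails here, because the record is missing precisely because the value is zero.

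A zero baseline causes a second problem: the ratio is undefined at every cycle, so the patient contributes nothing.

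At stake is a formal between-arm comparison of parameters that the SAP models because they bear on disease status. A near-null blast result beside a positive remission rate would be an artefact of the transformation, and readers could take it for a finding.

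**Working it through.** The documents give no figure for this model, so there is none to reproduce. The check asks how many records are exposed and what losing them does.

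**Inputs from the documents.** Allocation 40 to LY3039478 and 20 to placebo; assumed CR plus CRi rates 40% and 5% (Protocol 12.1, SAP 5.2).

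**Assumptions not in the documents.** Baseline circulating blasts log-normal with median 5 in arbitrary units and log SD 1.2; floor f for a zero of 0.1, 0.05 or 0.01 in the same units; active-to-placebo ratio g among nonresponders from 0.5 to 1.3; placebo nonresponders unchanged on average.

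**Step 1: patients exposed.** If every responder has T-ALL, 40 × 0.40 = 16 against 20 × 0.05 = 1, or 17 of 60 (28%). T-LBL responders would lower this. Partial remission could add zeros, since Protocol 10.1.3.1 asks PR patients to meet the hematologic values for CR.

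**Step 2: one cycle.** With zeros dropped, only nonresponders remain and the geometric mean ratio is g. With zeros kept at floor f, a responder's mean log ratio is ln(f/5), so

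ratio = g^0.60 × (f/5)^(0.40 − 0.05).

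For g = 1 this gives 0.02^0.35 = 0.25, 0.01^0.35 = 0.20 and 0.002^0.35 = 0.11. Simulated averages agree with the formula to within 0.01:

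| g in nonresponders | Zeros dropped | Kept, f = 0.1 | Kept, f = 0.05 | Kept, f = 0.01 |
|---|---|---|---|---|
| 0.5 | 0.50 | 0.17 | 0.13 | 0.08 |
| 0.7 | 0.70 | 0.21 | 0.16 | 0.09 |
| 1.0 | 1.0 | 0.25 | 0.20 | 0.11 |
| 1.3 | 1.3 | 0.30 | 0.24 | 0.13 |

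Dropping zeros hides most of the difference in the first three rows and reverses its sign in the last. Across each row, the answer also depends heavily on the floor.

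**Step 3: repeated measures.** A random-intercept model over three cycles approximates the planned model (100 simulated trials, g = 1, responders reaching zero at cycle 1 or 2). The cycle-3 ratio is 0.81 with zeros dropped and 0.10 with zeros kept at 0.01. Responders' earlier non-zero visits stay in, so the loss is less than total.

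**Step 4: no floor.** Suppose a normal latent log ratio has 40% and 5% below the detection point. The true shift is z(0.40) − z(0.05) = −0.253 + 1.645 = 1.392 SD. The mean of the values above that point is −1.392 + 0.386/0.60 = −0.748 on LY3039478 and 0.103/0.95 = 0.109 on placebo, a difference of 0.856 SD. About 0.856/1.392 = 62% of the log effect remains.

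**Step 5: direction.** Suppose 40% of patients are sensitive. On LY3039478 all of them reach zero. On placebo 5% of all patients reach zero and the other 35% halve their blasts. The resistant 60% rise 1.5-fold in both arms. With zeros dropped, the placebo mean log ratio is (0.35 × ln 0.5 + 0.60 × ln 1.5)/0.95 ≈ 0.001, against ln 1.5 on LY3039478. The ratio is 1.50, favouring placebo although LY3039478 cleared far more patients.

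**The case against.** The strongest reply is that the SAP nowhere says zeros are excluded. If laboratories report absent blasts as <x, the existing rule keeps remission visits in. SAP 6.1 also allows alternative or nonparametric methods. This stands in part: record loss is an inference about how the log step would run. But Protocol Attachment 2 places blasts under a manual differential, where absence is naturally recorded as 0, and hematology is assigned to both local and sponsor-designated laboratories, so formats could differ. Imputing to a quantification limit is itself a floor, and step 2 shows how much the floor matters. The SAP 6.1 fallbacks are general and would leave the choice until the data are seen.

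A reader might infer several stronger points that the documents do not support:

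- **That every blast or rare-cell count is zero by definition in remission.** Only circulating blasts in T-ALL CR and CRi are. Marrow blasts need only be below 5%. Eosinophils, basophils and NRBC may be zero, but no section says remission makes them so.
- **That responders leave the analysis.** Only their zero visits would, unless baseline is also zero, and the documents do not tie a zero baseline to later response.
- **That the bias is always toward no difference.** Step 5 and the g = 1.3 row show otherwise.
- **That a ratio near 0.1 or 0.2 is the true effect.** It follows from the assumed floor and baseline.

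It is also fair to say that the model is supportive and that remission rates and the marrow-blast waterfall plot capture blast clearance separately.

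**Conclusion.** The concern holds in a limited form. SAP 6.14.4 prescribes a calculation that is undefined at zero, for a list that includes an analyte whose zero is part of T-ALL CR and CRi, and its substitution rule does not reach a recorded 0. If zeros become missing, records are lost in an outcome-dependent way, for up to about 16 of 40 against 1 of 20 CR/CRi responders at the planned rates. That count assumes all responders have T-ALL, had non-zero baseline blasts and have absence recorded as 0. The between-arm blast comparison would then be biased, usually but not always toward no difference. The size cannot be fixed from the documents: the illustrations range from 62% of the log effect retained to a reversal of sign.

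ORR by Fisher's exact test, EFS and OS do not use this model. The point should be corrected, but it does not threaten the trial's main conclusions.

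**What to change.** In SAP 6.14.4, for circulating blasts and any analyte with recorded zeros at baseline or later (including neutrophils if zeros occur):

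1. Make the main between-arm comparison the proportion at zero by cycle, with its denominator stated, plus a rank-based analysis.
2. Use a log model with a substituted floor only as a sensitivity analysis, apply the floor at baseline too, and show at least two floors because the result depends strongly on that choice.
3. State how an absent count is recorded, so that 0 and <x are treated alike across laboratories.
4. Keep the log-ratio mixed model for analytes that are always positive.

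The cost is a few sentences in the SAP and slightly more analysis. The downside is that blasts will have no single geometric mean ratio as their headline summary.

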#### **6.14.5. Vital Signs and Other Physical Findings**

Vital signs measurements including height, weight, temperature, blood pressure and post-baseline ECOG or Lanksy performance status will be listed by treatment arm.

#### **6.14.6. Electrocardiograms**

Electrocardiogram (ECG) assessment of normality and clinical significance will be listed by treatment group. Myocardial information and quantitative results including PR, QRS, QTcB (Bazett's correction), QTcF (Fridericia's correction) and RR intervals will be provided in patient listings for absolute and change from baseline. In addition, summaries of outlying corrected QT intervals (QTc, QTcB and QTcF) will be provided by treatment. Outlying intervals include absolute values  $> 450$ ,  $> 480$  and  $> 500$  msec and change from baseline  $> 30$  and  $> 60$  msec.

Further exploratory analyses may be conducted as warranted.

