10.3.1.2. Suspected Unexpected Serious Adverse Reactions

Suspected unexpected serious adverse reactions (SUSARs) are serious events that are not listed in the DCSI of the IB and that the investigator identifies as related to the investigational product or study procedure. United States 21 CFR 312.32, European Union Clinical Trial Directive 2001/20/EC and the associated detailed guidances or national regulatory requirements in participating countries require reporting of SUSARs. Lilly has procedures that will be followed for the recording and expedited reporting of SUSARs that are consistent with global regulations and associated detailed guidances.

10.3.2. *Electrocardiograms*

For each patient, 12-lead digital ECGs will be collected as replicates (usually triplicates) according to the Study Schedule ([Attachment 1](#)). Patients must be supine for approximately 5 to 10 minutes before ECG collection and remain supine but awake during ECG collection.

Consecutive replicate ECGs will be obtained at approximately 1-minute intervals. ECGs may be obtained at additional times, when deemed clinically necessary. Collection of more ECGs (more replicates) than expected at a particular time point is allowed when needed to ensure high quality records.

ECGs will initially be interpreted by a qualified physician (the investigator or qualified designee) at the site as soon after the time of ECG collection as possible, and ideally while the patient is still present, to determine whether the patient meets entry criteria at the relevant visit(s) and for immediate patient management, should any clinically relevant findings be identified.

After enrollment, if a clinically significant increase in the QT/QTc interval from baseline or other clinically significant quantitative or qualitative change from baseline is identified, the patient will be assessed by the investigator for symptoms (eg, palpitations, near syncope, syncope) and to determine whether the patient can continue in the study. The investigator or qualified designee is responsible for determining if any change in patient management is needed and must document his/her review of the ECG printed at the time of evaluation from at least 1 of the replicate ECGs from each time point.

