PK Sample Number	Cycle	Day	PK Sampling Time for LY3039478/ Placebo ^b	PK Sampling Time for Dexamethasone ^b	PD Sampling Time for NICD and Gene Expression ^c	ECG ^a and ECG Chemistry
1	1	1	Predose	Predose	Predose	Predose
2	1	1	1-3h	1-3h		1-3h
3	1	1	6-8h	6-8h	6-8h	
4	1	15	Predose	Predose		
5	1	15	1-3h	1-3h		
6	1	15	6-8h	6-8h		
7	2	1	Predose			Predose

Abbreviation: ECG = electrocardiogram; NICD = Notch intracellular domain; PD = pharmacodynamic; PK = pharmacokinetic.

a ECG required for all patients.

b Samples of approximately 3 mL of whole blood will be collected for measurement of LY3039478 and dexamethasone in Cycle 1 only. On other days, 2 mL of whole blood will be collected for measurement of LY3039478.

c NICD collection will be performed at select sites only.

Note: Collection of PD samples, where similar intervals are presented, should be collected the same time as PK samples.

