## 6. A Priori Statistical Methods

### 6.1. General Considerations

Phase 1 Part A, Phase 1 Part B and Phase 2 study parts will be reported in separate TFLs.

Results of descriptive analyses and estimates from inferential analyses will be presented by dose level cohort (phase 1) or by treatment (phase 2). In the phase 2 study part, an additional group will be included in primary efficacy and safety TFLs to represent data for patients receiving LY3039478 in combination with dexamethasone after failure of placebo in combination with dexamethasone.

All tests of treatment effects will be conducted at a 2-sided alpha level of 0.05, unless otherwise stated. All tests of interactions will be conducted at a 2-sided alpha level of 0.1, and all CIs will be given at a 2-sided 95% level, unless otherwise stated.

The assumptions for each statistical method will be evaluated. If there is violation of assumptions, alternative statistical methods may be used.

Additional exploratory analyses of the data will be conducted as deemed appropriate.

For continuous variables, summary statistics will include number of patients, mean, median, standard deviation, minimum, and maximum. Categorical endpoints will be summarized using number of patients, frequency, and percentages. Any missing longitudinal data will not be imputed, rather estimated from an appropriate random mixed effects model. Transformations will be applied where assumptions behind any analysis are better satisfied by data being transformed onto an alternative scale. All results from any of these analyses will be back transformed to the original scale. Alternatively, nonparametric methods will be applied.

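### SAP 6.14.6 commits to QTc by arm only as outlier counts, so no between-arm QTc estimate is prespecified and a 10 msec mean shift would usually be missed (assumed SD 12-20 msec)

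*SAP*

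**What the plan says.** - **Continuous values.** SAP 6.14.6 says that PR, QRS, QTcB, QTcF and RR "will be provided in patient listings for absolute and change from baseline".
- **By arm.** The same section continues: "In addition, summaries of outlying corrected QT intervals (QTc, QTcB and QTcF) will be provided by treatment". The cuts are above 450, 480 and 500 msec, and changes above 30 and 60 msec. It names no test, mean, model or interval.
- **Open clauses.** SAP 6.14.6 ends: "Further exploratory analyses may be conducted as warranted". SAP 6.1 has a general rule: "For continuous variables, summary statistics will include number of patients, mean, median, standard deviation, minimum, and maximum". Protocol 12.2.12 (Safety Analyses) adds no ECG analysis.
- **Data available.** Under Protocol 10.3.2, "12-lead digital ECGs will be collected as replicates (usually triplicates) according to the Study Schedule". In Attachment 3, the Phase 2 sampling table is headed as covering about 30 patients, but its footnote states "ECG required for all patients". ECGs fall before dosing and 1-3 h after dosing on Cycle 1 Day 1, and before dosing on Cycle 2 Day 1.
- **Contrast.** SAP 6.14.4 gives laboratory values a repeated-measures model with treatment comparisons and 95% CIs at each cycle.

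**The concern.** Dichotomizing a continuous safety measure at high cuts discards most of the information about a shift in its mean. With 40 v 20 patients, few or none may cross a cut in either arm even when the active arm has moved by a moderate amount. The measurement most directly suited to the question is the randomized, placebo-controlled difference in change from predose. It is collected, yet the plan commits to showing it only patient by patient.

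At stake is what the study report can say about QTc from a prespecified analysis. Sparse counts are weak evidence of an effect and equally weak reassurance that there is none. A mean difference with an interval at least shows which effects the data are compatible with.

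**Working it through.** **Inputs.** Arms of 40 and 20 (SAP 5.2), two-sided alpha 0.05 (SAP 6.1), cuts from SAP 6.14.6. Assumed, because the documents do not give them: true mean shift δ = 10 msec, SD of change σ = 12 to 20 msec, normal changes, complete data.

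**The plan's own figure.** None is stated for QTc. The only power figure in the documents is about 82% for remission rate. Exact enumeration of the stated Fisher test gives 87.8% (87.7% with the futility rule applied). It has no bearing on this point.

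**Change cuts, one post-dose reading.** P(change > c) is 1 − Φ((c − δ)/σ) on active and 1 − Φ(c/σ) on placebo. For σ = 15 and c = 30: 1 − Φ(1.33) = 9.1% v 1 − Φ(2) = 2.3%. Fisher power sums the two binomial probabilities over all tables with two-sided p ≤ 0.05 and the higher proportion on active.

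**Mean change.** SE = σ√(1/40 + 1/20) = 0.274σ. Power comes from the noncentral t on 58 df with noncentrality 10/SE, and the 95% CI half-width is 2.002 × SE. For σ = 15: SE = 4.11, noncentrality 2.43, power 67%, half-width 8.2.

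| SD (msec) | >30 msec, active v placebo | Expected counts | Fisher power, >30 | Fisher power, >60 | Power, mean difference | CI half-width (msec) |
|---|---|---|---|---|---|---|
| 12 | 4.8% v 0.6% | 1.9/40 v 0.1/20 | 0.05% | about 0% | 85% | 6.6 |
| 15 | 9.1% v 2.3% | 3.6/40 v 0.5/20 | 1.7% | about 0% | 67% | 8.2 |
| 20 | 15.9% v 6.7% | 6.3/40 v 1.3/20 | 9.0% | about 0% | 43.5% | 11.0 |

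For a 15 msec shift the corresponding ranges are 5-29% on change >30 msec and 77-99% for the mean.

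**All five cuts, Phase 2 schedule.** This was simulated with the full 10 msec effect at 1-3 h on Cycle 1 Day 1 and none at Cycle 2 Day 1 predose. Each patient's larger value was used. Further assumptions: between-patient baseline SD 20 msec and correlation 0.5 between the two changes. For baseline means of 410-430 msec and SD of change 8-20 msec, the chance of a significant imbalance on any cut was 0.7% to 12.5% (5,000 trials per setting). A repeat with 20,000 trials gave 0.8% to 13.0%. At SD 8 and 10 all of this came from the 450 msec cut.

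**A check that needs no SD.** With 0/20 placebo patients above a cut, 8/40 active patients are needed for p ≤ 0.05 (p = 0.043; 7/40 gives 0.084). With 1/20, it takes 11/40.

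**The case against.** **No test is planned on the counts.** This stands: Fisher power is a yardstick for how far the counts can separate the arms. At SD 20 the expected pattern, about 6/40 v 1/20, would be visible to a reader without a test.

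**A reader might infer that a 10 msec effect would almost never show.** The documents do not support that. They give no SD, no baseline mean and no rule for combining replicates. The absolute cuts add some sensitivity: for a single reading carrying the full effect and a baseline mean of 430 msec, power on >450 msec is 14-27%. With the full effect at three independent post-dose readings, the chance on any cut is 9-47%, but the Phase 2 schedule has one post-dose reading and one on-treatment predose reading.

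**A reader might also infer that the ECG data could support no statement about QTc.** That is not supported either. The values are listed, further exploratory analysis is allowed, and Protocol 10.3.2 has the digital ECGs stored centrally. A mean could be computed later, although post hoc. The general rule in SAP 6.1 lists mean and SD for continuous variables but is not tied to ECGs, and SAP 6.14.6 assigns those values to listings.

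**Prior concern is low.** QTc is not a study objective. Protocol 5.1.5 expects no hERG-mediated QT risk and reports no ECG effect in the dog study. Protocol 5.1.6 names no QT event among common related events or dose-limiting toxicities. This keeps the point minor.

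**The remedy has limits.** Protocol 5.1.4 gives a nonclinical half-life of 2-6 h, so Cycle 2 Day 1 predose may carry little drug effect. Protocol 5.2 describes rapid progression, so numbers may also have fallen by then. At SD 20, with no true effect, the interval would exclude 10 msec in only about 44% of trials.

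**Conclusion.** The gap is real but small. SAP 6.14.6 commits to no between-arm estimate of QTc change, and neither open clause supplies one. The outlier counts would usually miss a 10 msec mean shift that the difference in mean change is far better placed to detect: at most 9% against 44% at SD 20, and 0.05% against 85% at SD 12. These figures rest on an assumed SD of 12-20 msec, normal changes and complete data in 40 v 20 patients; the five-cut figure also rests on assumed baseline QTc and correlation. The direction holds across that SD range, but the exact size cannot be fixed from the documents. Nothing is lost irretrievably, and no primary or secondary efficacy conclusion is affected.

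**What to change.** In SAP 6.14.6:

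- Add a by-arm table of mean change in QTcF from predose Cycle 1 Day 1, with the between-arm difference and 95% CI from ANCOVA on predose QTcF.
- Make 1-3 h on Cycle 1 Day 1 the main time point and Cycle 2 Day 1 predose supportive.
- Average the replicates at each time point before both the mean and the outlier analyses. The SAP is silent on this, and the counts depend on it.
- Say what the unlabelled QTc is, since it is listed separately from QTcB and QTcF.
- Keep the outlier table.

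The cost is one extra table and a few lines of text, with no new ECGs. The downside is an interval that may be too wide to exclude 10 msec if the SD is near 20 msec; the text should say so in advance.
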